The study will be conducted in Johannesburg, South Africa at one or more large HIV public sector sites. One such site will be the Themba Lethu HIV clinic, a comprehensive care management and treatment site in Gauteng Province. Themba Lethu is a large HIV testing, care, and treatment site located at the Helen Joseph Hospital. Themba Lethu is one of the largest HIV clinics in South Africa as it has initiated > 30,000 adult patients on ART. If a sufficient number of women are not eligible to enroll in the study at TLC, then other suitable HIV clinics in Gauteng will be identified and included in the study.

b. Inclusion and Exclusion Criteria

Study participants will be adult women who are HIV positive, have initiated HIV treatment, have an unsuppressed viral load or who have defaulted from treatment since their last viral load, and have experienced intimate partner violence (IPV). Participants will be recruited by study staff after a warm hand-off referral from clinic staff. We will also enroll their male partners if the woman chooses to include them. The minimum age of research subjects will be 18. All subjects will be recruited from HIV clinics.

Patient inclusion criteria will be:

- Adult HIV positive women \geq 18 years old

- Initiated HIV treatment
- Most recent viral load >50 copies/mL, have defaulted from treatment or had a missed or late (>14 days) visit in the last year
- Has experienced IPV in the past 12 months
- Has their own phone and can receive text messages
- Literate and able to speak and read one of: English, Zulu, SeSotho
- If including a partner, the woman has disclosed HIV status to the partner that will be invited to participate

Exclusion criteria will be:

- Unwilling to complete the informed consent process
- Currently psychotic or on unstable psychiatric regimen
- Suicide attempt/ideation with intent and plan, and/or self-harm in the past month
- Enrolled in any other HIV treatment intervention study

For Men, the inclusion/exclusions criteria will be

Male inclusion criteria will be:

- Adult \geq 18 years old
- Invited by partner to be in the study
- Partner has disclosed their HIV status
- Has their own phone and can receive text messages
- Literate and able to speak and read one of: English, Zulu, SeSotho

Exclusion criteria will be:

- Unwilling to complete the informed consent process
- Currently psychotic or on unstable psychiatric regimen
- Suicide attempt/ideation with intent and plan, and/or self-harm in the past month

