After subjects' consent for the study they will be screened for eligibility. The screening questionnaire will contain questions related to mental health, experiences with intimate partner violence and experiences with HIV care and ART initiation. If eligible, and the participant agrees to the second informed consent, participants will be administered a baseline questionnaire. The study instrument, called the Client Monitoring Form (CMF), will be administered to clients using a tablet which allows the responder control to navigate and ability to answer sensitive questions privately and discreetly. The assessment asks questions about symptoms related to common mental and behavioral health problems. It will be kept in a password protected database with identifiers removed. Data collected will be electronically transferred from the field devices into the study database at HE²RO offices daily. Data on the devices will then be permanently deleted. Data will be securely transferred to BU and JHU weekly.

iii. Intervention records

Intervention data will be maintained for all participants in password protected databases. The data will include no identifying information about the client, only his/her study ID number. These data will include:

- Dates, times and SMS messages sent for both arms
- Attendance at CETA sessions (both in person and T-CETA)
- Weekly checks of symptom severity (e.g., substance use, mental health)
- Clinical notes recorded after each session by the peer educator
- Responses to the weekly safety questions and any additional notes on safety

iv. Focus Group Discussion and In-depth Interviews

For the CETA user insights, FGD's and IDI's will include CETA treatment arm study participants from Zola CHC, who completed the intervention in 2023. Participants need to have participated in at least 5 CETA sessions.

For insights from CETA providers and facility healthcare providers from both study sites (Themba Lethu clinic and Zola CHC). We will also conduct IDI's, with CETA providers, who need to have conducted CETA sessions for the duration of the study, and with healthcare providers who were part of the CETA study's referral of participants and know about the CETA study.

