REDCap or a similar software program requiring secure log-in and access by invitation will be used to create an electronic database to manage any quantitative study data not entered directly into tablets. The database will be used by field staff to double enter data where necessary. Data files will be reviewed by the study team on a monthly basis and queries returned to the site-level staff for response. On a regular basis, the data will be converted to SAS, STATA or SPSS for final cleaning and data analysis. All analytic databases will be password protected with access restricted to the members of the study team.

DATA ANALYSIS

a. Primary Outcome

Our primary outcome is the proportion of participants who are retained and suppressed by 12 months post randomization(34,82). Viral load testing is routinely done at the clinic at 6- and 12-months post ART initiation and every 12 months thereafter. Due to the variability in when viral load testing is done, we will define the primary outcome to be suppression (i.e. a viral load <50 copies/mL) any time up to 18 months. As our primary outcome includes retention, we are not able to contact patients who miss routine viral loads as this would affect attrition. Instead we will use routine clinic data collection (as we have done in the past (83–86)) to determine outcomes. Missing viral loads will be a negative outcome.

b. Secondary Outcomes

- Viral suppression at 3 and 24 months: CETA may have some effects on suppression and retention over the first year on treatment mediated through the increased contact with patients that CETA

entails. It is not clear for how long after the CETA intervention effects will be sustained. Thus, we will look at suppression at 24 months, long after CETA is complete. As our population should be monitored for suppression more frequently than every 12 months, we will also examine suppression within 3 months.

- Attrition at 12 and 24 months - Attrition (the opposite of retention) will be defined as being more than 90 days late for a study visit.
- IPV, mental/behavioral health, alcohol and other substance use: We will measure the effectiveness of CETA in reducing IPV and stress-related problems commonly associated with IPV and HIV, mental health (trauma, depression, anxiety), and alcohol and substance use. We will also assess whether a change in these factors mediates the effectiveness of CETA on the primary outcome.

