- Cost and cost-effectiveness: We will estimate the incremental cost-effectiveness of CETA versus active control in achieving the primary study outcome, retained in care and virally suppressed by 12 months, from the provider perspective. If found to be effective, a budget impact analysis will be conducted to estimate the affordability of routine implementation of the intervention at scale.
- Perceptions and acceptability of CETA: Using qualitative focus group discussions and in-depth interviews with both study participants in the treatment arm, CETA providers and healthcare providers. we will also explore the perceptions, acceptability and durability of the intervention, both as a recipient of care and provider and also the feasibility of delivering this intervention which will help inform recommendations for further implementation and scale up of the intervention, which will help inform recommendations for further implementation and scale up of the intervention.

c. Sample Size

Based on the ENHANCE study(85), we estimate that only 40% of those who are unsuppressed will be retained in care and virally suppressed 12 months post-baseline in the control arm. We believe a 20% increase in the percent suppressed and retained between the CETA and control arms would be clinically meaningful. Our primary aim is to analyze the impact of CETA in the full population; however, we have calculated our sample size to ensure our ability to detect differences separately among women who include a partner. With 80% power and 2-sided $\alpha=0.05$, using a chi-squared test for independent proportions our sample size required is 91 per arm (182 total). To have power to detect mediators and moderators (Aim 2), we will increase the sample size to **400 total** with a minimum of 75 women in the CETA arm who include partners (max of 100), which will give us 80% power to detect an absolute 21% difference between arms in women with partners. To get 75 women who include partners in the CETA arm we will have to randomize about 150 women willing to include a partner if randomized to CETA. We will also include at least 75 partners of women, up to 100.

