Themba Lethu clinic alone has about 4000 female patients, while other clinics have similar numbers of patients. Of these, about 1000 had an unsuppressed viral load in the past year. We anticipate that 50% of those we screen will be eligible for the study and of those 50% will enroll. We therefore estimate we will need to **screen approximately 1600 patients** over 18 months, requiring us to screen about 20 patients and enroll approximately 5 patients per week over the enrollment period.

Given we are randomizing 400 women and including up to 100 men, the total sample size for the IRB will be 500.

The IPV literature strongly suggests that more needs to be done with perpetrators of violence (not just survivors), and we know from studies like ours in Zambia that helping male partners led to many positive changes on outcomes, and from the perspective of the women. However, for this study, we wanted the choice to be the womans' – for ethical and safety reasons. Therefore, we could not confirm the ultimate number of male participants we would have.

Sample Size – Qualitative Study Component

For the FGDs and IDIs we will purposively select participants from the main study. We will recruit a total of 40 participants from the treatment arm who completed the trial in 2023. There will be 3 FGDs, with 6-10 participants in each FGD, and 10 IDIs with study participants. We will also recruit 5 CETA providers and 5 healthcare providers who supported referral to CETA from Themba Lethu Clinic and Zola clinic (adherence counselors), for in-depth interviews.

d. Primary Analysis

All primary analyses will be by intention-to-treat. The unit of analysis will be the woman. Our primary analysis will be a comparison of risk differences with 95% confidence intervals. If we identify differences (RD) in baseline covariates we will conduct an adjusted linear regression to get an adjusted RD.

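### The primary risk difference is adjusted only if chance imbalance is seen; prespecifying adjustment for baseline viral load status is a free, modest gain in precision and removes an open choice

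*Combined protocol and SAP*

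**What the plan says.** Under Data Analysis, d. Primary Analysis, all primary analyses are by intention to treat and "Our primary analysis will be a comparison of risk differences with 95% confidence intervals". The rule on covariates is one sentence: "If we identify differences (RD) in baseline covariates we will conduct an adjusted linear regression to get an adjusted RD".

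The inclusion criteria give three alternative routes on HIV status: "Most recent viral load >50 copies/mL, have defaulted from treatment or had a missed or late (>14 days) visit in the last year". Only the first requires an unsuppressed result. The same list appears under Ethical Considerations.

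Under a. Primary Outcome, the outcome combines retention with suppression; because of variable test timing "we will define the primary outcome to be suppression (i.e. a viral load <50 copies/mL) any time up to 18 months", and "Missing viral loads will be a negative outcome".

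Under c. Sample Size, the control rate is tied to one part of this population: "we estimate that only 40% of those who are unsuppressed will be retained in care and virally suppressed 12 months post-baseline".

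Other relevant provisions:

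- Randomization is blocked; no stratification factor is stated.
- The qualitative section refers to providers "from both study sites (Themba Lethu clinic and Zola CHC").
- The Clinic Records section lists viral load results and dates among the data taken at baseline and up to 24 months.
- The Moderator Analysis names absence of viral suppression as a potential moderator, with RDs within moderator levels.

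**The concern.** In a properly randomised trial, baseline differences between arms arise by chance. Under the stated rule, the observed data decide both whether to adjust and for what. The result can be two RDs for the primary outcome, with nothing to say which one carries the conclusion.

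The rule also passes over a covariate that is very likely to matter. The outcome includes a viral load below 50 copies/mL, and the entry criteria produce a mix of women above that level and women already below it. Baseline status should therefore predict the outcome, yet the plan uses it only as a moderator. Without stated stratification, its balance is left to chance. At stake are the width of the primary confidence interval and an unambiguous primary result.

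**Working it through.** **The plan's own figure.** The Sample Size section gives 91 per arm for 80% power, two-sided 0.05. Reading the 20% increase as 40% versus 60%, the pooled chi-squared formula gives 97 per arm, and power at 91 is 77.4%. That mismatch is a separate matter: at the planned 200 per arm, power for 40% versus 60% is 98.1%.

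**Inputs from the documents.** 400 women, 1:1; 40% control success among unsuppressed women; missing viral load counted as failure, so no loss of denominator.

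**Assumed inputs, not in the documents.** Share suppressed at entry, s: 10 to 50%. Control success among them, q: 50 to 80%. True RD: 10 points in both groups.

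**Formulas.** In each arm, with suppressed success a, unsuppressed success b and marginal m = s·a + (1−s)·b:

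- unadjusted variance of RD = [sum over arms of m(1−m)] / 200
- adjusted variance of RD = [sum over arms of s·a(1−a) + (1−s)·b(1−b)] / 200

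**Middle case, s = 0.25, q = 0.70.**

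- Marginals: control 0.25×0.70 + 0.75×0.40 = 0.475; CETA 0.575.
- Unadjusted: (0.2494 + 0.2444)/200 = 0.002469, SE 0.0497.
- Adjusted: control 0.25×0.21 + 0.75×0.24 = 0.2325; CETA 0.25×0.16 + 0.75×0.25 = 0.2275; sum 0.460/200 = 0.0023, SE 0.0480.
- Reduction: 1 − 0.460/0.4938 = 6.8%. The 95% half-width goes from 9.7 to 9.4 points.

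| s | q | SE unadjusted | SE adjusted | Variance reduction | Effective N | Power |
|---|---|---|---|---|---|---|
| 10% | 50% | 0.0496 | 0.0495 | 0.4% | 401 | 52.3% to 52.4% |
| 25% | 70% | 0.0497 | 0.0480 | 6.8% | 429 | 52.1% to 55.0% |
| 50% | 80% | 0.0474 | 0.0430 | 17.8% | 486 | 55.9% to 64.2% |

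**Site.** With two equal sites around 40% and a site difference d, the reduction is (d/2)²/0.24: 0.3% for d = 5 points, 4.2% for d = 20 points. Most of the gain comes from suppression status.

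**Simulation.** 20,000 trials per scenario, N = 400, linear model with robust SE. The prespecified version adjusts for baseline suppression and site. The triggered version adjusts only when baseline suppression is significantly imbalanced (an assumed trigger, since the plan gives none).

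| Power at RD = 10 points | Unadjusted | Prespecified | Triggered |
|---|---|---|---|
| Middle case | 52.4% | 55.0% | 52.5% |
| Top case | 55.8% | 63.6% | 56.4% |
| Status not prognostic | 51.7% | 51.5% | 51.7% |

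Type I error was 5.0 to 5.1% with prespecified adjustment and 4.5 to 5.0% with triggered adjustment. It reached 6.3 to 6.9%, when status was prognostic, only if the more significant of the two RDs was the one reported. Where status was not prognostic, the empirical SD was 0.0498 unadjusted and 0.0499 adjusted.

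**The case against.** The strongest reply is that the plan states the RD comparison without condition as the primary analysis, so the adjusted RD can be read as supplementary. That reading is available, but the text does not settle it, and under it the precision is simply given up.

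The size is also open to challenge. Reckoned from the control arm alone, assumed scenarios of 20 to 50% suppressed with 70 to 85% success suggest a gain worth 6 to 28% more women. If CETA adds 20 points only among unsuppressed women, that gain falls to about 3 to 16%, because the contrast between the groups shrinks in the CETA arm. None of these inputs is in the documents, so only a range can be claimed.

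A reader might infer more than the documents support:

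- **That triggered adjustment inflates type I error.** It did not in the simulation. Inflation needs selective reporting, which the plan does not propose.
- **That suppressed women cannot benefit, so the trial is underpowered.** If they gained nothing, a 20-point effect in the rest would give a pooled 14 points at 30% suppressed (0.7×20) or 10 points at 50%. But the outcome also needs retention and counts a missing test as failure, and these women enter through default or visit problems. Zero benefit is a bounding assumption, and adjustment would not cure dilution.
- **That baseline status is known for everyone.** Routine tests fall at 6 and 12 months after ART initiation and then yearly, so recent starters may have none and defaulters an old one.
- **That results by baseline suppression are missing.** The Moderator Analysis provides for them.

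Robust standard errors are stated only for the continuous outcomes, but with 1:1 allocation this makes practically no difference.

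Timing stands as a caution: the monitoring plan records one-year follow-up as complete by March 2025, and the study is not blinded.

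**Conclusion.** The point holds as a free improvement. The stated rule makes adjustment depend on chance imbalance, names no covariate and leaves open which RD is primary. Prespecified adjustment for baseline viral load status is better: under the assumed inputs it lowers the variance by about 0 to 18%, roughly 7% in the middle case, at negligible cost if status is not prognostic. The gain is modest, comes mainly from suppression status rather than site, and its direction depends on that status being prognostic. The harm of the present rule is forgone precision and undefined discretion, not a demonstrated bias or excess of false positives. Separately, the 40% planning rate describes unsuppressed women, whereas the eligible population is wider.

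**What to change.** Before any comparison by arm, state in the SAP:

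1. The single primary estimate is the RD from a regression (linear, or binomial with identity link) with robust standard errors, on arm and baseline viral load status, fitted whatever the observed balance. Site may be added.
2. Baseline status has three categories: above 50 copies/mL, suppressed, and missing or older than a stated window. Assign a value of exactly 50, which falls between the eligibility and outcome definitions.
3. The unadjusted RD is a sensitivity analysis.
4. The 40% planning rate refers to unsuppressed women only. RDs by baseline suppression remain as already provided for under moderators.

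Date the change. If data by arm have already been seen, label it post hoc.

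The cost is SAP wording and a coding rule for old or missing tests; no new patients or data collection are needed.

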The full consent process, including signed informed consent, will be administered by a trained study staff member. The study staff will emphasize the voluntary nature of the study. The full consent form, for those who are eligible and interested in being in the study, will describe the nature and goals of the study and assure subjects their information will be kept confidential. We will explain to subjects the possible treatment options in the study and that they will not get to decide which group they will be in, but rather that we will decide by chance and they will have a 50-50 chance of being in either group. We will explain that if they are randomized to the intervention arm (CETA) their care will be different from the active control (text+safety) arm and the options they have to not participate. It will also be explained that they will be free to withdraw from the study at any time with no risk to the healthcare they receive at the clinic. The consent process will take place in a private space and women will be given adequate time to decide whether they want to participate and will be allowed to leave the clinic and return at a later time to complete the consent process if they choose to. Consent documentation will be done either using a paper form or via electronic consent by having the participant sign the document in REDCap. If an electronic signature is used, it will be on a PDF version of the IRB approved and stamped consent form. This will be done via a tablet in person (as would be done for a paper consent) and the participants will have access to the consent form as the consent process is taking place. Even if participants sign the consent electronically, they can also have a paper copy of the information sheet. As such, no electronic version of the e-consent will be made available to the participants.

For safety reasons, we will inform women that they do not need to take a copy of the consent form if they do not wish to do so in order to minimize disclosure of information since the woman's consent form includes experience with violence.

The consent form will include permission to access their clinic records. The consent form will also state that the subject agrees to complete a baseline questionnaire for our study and that the questionnaire responses can also be linked to the subject's treatment records. Participants will be assured that data

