At the clinic, study staff will have a randomization code within the tablet system used for data collection. Following completion of the baseline assessment, the computer will generate the next randomization group. Randomization will be blocked to ensure that roughly equal numbers end up in each arm. The computer will also generate the randomization assignment for the Randomization ID assigned to the patient (and subsequently linked with their Screening ID). Randomization IDs and assignments will be generated *a priori* by a U.S.-based study team member and linked into the computer system. We will inform the participant of their assignment immediately after the baseline assessment. Those participants who are assigned to CETA will then be asked whether they want to invite a partner and if so, will be given the information sheet and forms to be completed and returned by their partner. Because randomization will occur only after the baseline assessment, some subjects may drop out before randomization, which will be tracked.

k. Study Arms: Common Elements Treatment Approach (CETA)

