At 3 months post-baseline (end of the CETA intervention) and 12 months post-baseline, participants will again complete the following tablet-based instruments: SVAWS, CES-D, HTQ, and ASSIST. Although the 3-month time-point could impact the primary retention-based outcome, we feel it is important given the dynamic nature of mental/behavioral problems, and any impact should be equal across arms. **With the exception of contacting participants for post-baseline assessments , qualitative data collection and safety checks, research staff will not contact participants for the reasons stated above.** This is essential for the trial given the intervention is designed to improve retention and viral suppression as well as reduce violence. Questionnaire data will also provide key patient-level data for evaluating costs and we will also collect resource utilization data (drugs, lab tests, supplies, staff cadre consulted etc.)

DATA SOURCES AND MANAGEMENT

a. Baseline and follow up data

At the baseline visit we will collect the following information:

- **Enrollment Information** (e.g., clinic ID, enrollment date, etc.)
- **Contact information** (e.g. phone number, address where they stay, who they share their household with)
- **Demographic information** (e.g., date of birth, sex, socioeconomic data, etc.)
- **HIV-related information** (only for women): (e.g., initiation date, ART regimen, pharmacy data, lab results, etc.)

At the baseline and at 3 and 12 months, participants will complete the following tablet-based instruments:

- **Severity of Violence Against Women Scale (SVAWS)**: 46 items assessing frequency of recent IPV. Subscales include: a) threats of violence (19 items); b) physical violence (21 items); and c) sexual violence (6 items). It was previously used in a study of IPV among women with partners who have alcohol abuse in South Africa(78).
- **Center for Epidemiological Studies-Depression Scale (CES-D)**: 20 items assessing frequency of depression symptoms over the past week (never, 1-2 days, 3-4 days, 5-7 days)(79).
- **Harvard Trauma Questionnaire (HTQ)**: 17 items assessing lifetime traumatic events. 39 items assessing post-traumatic stress symptoms in past week (not at all, a little, quite a bit, extremely)(80).
- **Alcohol, Smoking, and Substance Involvement Screening Test (ASSIST)**: A comprehensive assessment of substance use for a range of substance types(81) .

b. Primary outcome data

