We will analyze direct effects of CETA on continuous secondary outcomes (e.g., IPV [via SVAWS], mental health [via CES-D and HTQ], and substance use [via ASSIST score]) using linear mixed models. Fixed effects will include treatment arm, time, and arm X time interactions. Random effects will include participant ID to account for repeat measures. We will calculate robust standard errors. The models will estimate the difference in mean symptom change from baseline to each post-assessment between the treatment groups. The difference in mean change will be standardized to calculate Cohen's d effect size.

e. Moderator Analysis

In addition to main effects for the primary and secondary outcomes, we will evaluate the impact of potential moderators (e.g., lack of viral suppression, partner involvement, age, ethnicity, HIV knowledge and attitudes, education, physical health, duration on treatment, presence of side effects, regimen) on suppression and retention and mental health outcomes. An interaction between the moderator and treatment arm will be included in models described above. The interaction term will serve as the coefficient of interest in assessing whether treatment effects varied by levels of the moderator. For the effect of CETA by inclusion of partners we will compare women who included a partner in the CETA arm to those who said they would have included a partner in the control arm. Risk differences will be used to assess effect sizes within moderator levels.

f. Mediator Analysis

We will assess the role of potential mediating variables (IPV, mental health, substance use) on the impact of treatment on our primary outcome to tease out the direct and indirect effects of CETA. Several of the proposed mediators (e.g., interpersonal violence) may reasonably be expected to interact with the treatment arm to impact our primary outcomes. Invalid estimates may occur if this interaction is not considered in the mediator analysis. To allow for the possibility of exposure-mediator interactions, we will use a counterfactual approach and follow methods described by VanderWeele and Vansteelandt(87,88) and Valeri and VanderWeele(89). These methods are appropriate for both

continuous and binary mediators and outcomes and allow for estimating valid controlled direct effects as well as natural direct and indirect effects.

g. Cost Effectiveness Analysis and Budget Impact Analysis

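### The mixed model for the continuous secondary outcomes leaves baseline means free by arm although baseline precedes randomization; a common baseline mean would estimate the same effect more precisely

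*Combined protocol and SAP*

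**What the plan says.** All references are to the combined protocol and SAP.

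- **Model.** Data Analysis, d. Primary Analysis specifies linear mixed models for the continuous secondary outcomes: "Fixed effects will include treatment arm, time, and arm X time interactions". For the covariance it says "Random effects will include participant ID to account for repeat measures", which I read as one random intercept per woman. It adds "We will calculate robust standard errors".
- **Effect.** "The models will estimate the difference in mean symptom change from baseline to each post-assessment between the treatment groups". This implies that time is categorical. The result is then scaled: "The difference in mean change will be standardized to calculate Cohen's d effect size".
- **Visits.** Data Sources and Management, a. Baseline and follow up data: "At the baseline and at 3 and 12 months, participants will complete the following tablet-based instruments".
- **Order of events.** Study Procedures, j. Randomization: "Following completion of the baseline assessment, the computer will generate the next randomization group". The Full Consent section tells women "they will have a 50-50 chance of being in either group". Allocation is blocked, and no stratification on these scores is described.
- **What is absent.** No baseline constraint or baseline covariate is mentioned for these models. The adjusted analysis in the same section concerns the binary primary outcome. No SD, within-woman correlation, power or expected questionnaire dropout is given for any of the four scales.

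**The concern.** An arm main effect together with arm-by-time terms lets the two arms have different baseline means. With complete data and a random intercept, the arm-by-time term is then the raw difference in change scores. It subtracts the whole chance difference at baseline, when only the part that carries over to follow-up, a fraction ρ of it under equal SDs, should be removed. Both arms are drawn from one population and measured before allocation, so the model spends information on a quantity known by design to be zero.

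At stake is the precision of the second half of Aim 1, the effect of CETA on violence and on mental and behavioral health. The plan states no power for these outcomes, and some follow-up questionnaires will be missing, so precision available from data already collected has value. The binary primary analysis is not affected.

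**Working it through.** The plan gives no figure for these outcomes to reproduce; its sample-size section covers only the binary outcome. The check is therefore analytic, supported by generalized least-squares calculations.

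**Inputs from the documents:** three visits (0, 3, 12 months); 1:1 allocation; 400 women, so n = 200 per arm; baseline before randomization; a random intercept.

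**Assumed, because not stated:** ρ from 0.1 to 0.9; baseline/follow-up SD ratio r from 0.7 to 1.4; missing questionnaires at 3/12 months of 0/0, 10/20 or 20/40%.

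**Step 1. Equal SDs (σ), complete data.**

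- As planned: Var = (2σ²/n) × 2(1 − ρ).
- Common baseline mean: Var = (2σ²/n) × (1 − ρ²).
- Ratio: (1 − ρ²) / [2(1 − ρ)] = (1 + ρ)/2, so the reduction is (1 − ρ)/2.

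With n = 200, 2/n = 0.01. Standard errors (SE) are in SD units, and power is for an assumed effect of 0.25 SD:

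| ρ | SE planned | SE common baseline | Variance reduction | Power, planned → common baseline |
|---|---|---|---|---|
| 0.1 | 0.134 | 0.100 | 45% | 46% → 71% |
| 0.4 | 0.110 | 0.092 | 30% | 63% → 78% |
| 0.5 | 0.100 | 0.087 | 25% | 71% → 82% |
| 0.6 | 0.089 | 0.080 | 20% | 80% → 88% |
| 0.7 | 0.077 | 0.071 | 15% | 90% → 94% |
| 0.9 | 0.045 | 0.044 | 5% | about 100% for both |

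**Step 2. Missing follow-up (equal SDs).** Variance reduction at 3/12 months:

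| ρ | 0/0% missing | 10/20% missing | 20/40% missing |
|---|---|---|---|
| 0.4 | 30/30% | 28/26% | 26/21% |
| 0.5 | 25/25% | 23/21% | 21/17% |
| 0.6 | 20/20% | 18/17% | 17/14% |

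**Step 3. Unequal SDs (complete data).** Set the follow-up SD to 1 and the baseline SD to r.

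- Planned: variance proportional to 1 + r² − 2ρr.
- Common baseline, unstructured covariance: 1 − ρ².
- Common baseline, random intercept kept: 1 + w²r² − 2wρr, where w ≈ (2ρr + ρ)/(r² + 2).

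At r = 0.7 and ρ = 0.7 the planned value is 1 + 0.49 − 0.98 = 0.51 and the unstructured value is 1 − 0.49 = 0.51, so there is no gain.

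| r | ρ | Change in variance, random intercept kept | Change in variance, unstructured |
|---|---|---|---|
| 0.7 | 0.5 | −2% | −5% |
| 0.7 | 0.7 | +10% | 0% |
| 0.8 | 0.5 | −9% | −11% |
| 1.0 | 0.5 | −25% | −25% |
| 1.2 | 0.5 | −39% | −40% |
| 1.4 | 0.5 | −50% | −52% |

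Keeping the random intercept while imposing the constraint can therefore lose precision. The unstructured covariance does not, in large samples.

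**Step 4. Effect of chance imbalance.** Given an observed baseline difference D, the expected change-score estimate shifts by −(1 − ρ)D when SDs are equal. The SE of D is √(2/200) = 0.1 SD. A one-SE imbalance at ρ = 0.5 therefore moves the estimate by 0.5 × 0.1 = 0.05 SD. Averaged over randomizations the shift is zero.

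**The case against.** The strongest reply is that nothing here is wrong. The planned model is a conventional estimator of exactly the effect the plan says it will estimate, the outcomes are secondary, and no stated power is missed. That stands: this is an efficiency point.

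Three stronger readings are tempting, and the documents do not support them.

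- **A 20–30% gain for every scale.** This needs ρ between 0.4 and 0.6, equal SDs and near-complete follow-up on each scale at both visits. None of these is documented, and ρ may differ by scale and visit. For SVAWS the equal-SD assumption is doubtful, because women are selected on violence in the past 12 months and screened with its physical/sexual subscale.
- **No effort to keep women in the questionnaire follow-up.** Follow-up and Retention does disclaim retention efforts beyond outreach to complete CETA. But that section and the section on secondary outcome data both allow contact for the post-baseline assessments, and Costs and Payments reimburses 150 rand per study visit.
- **A change with no cost.** The Data Safety and Monitoring Plan records that all one-year follow-ups were complete by the DSMB sign-off in March 2025, and its Safety Review says the study is not blinded. Replacing the planned model now could cost credibility as a prespecified analysis unless it is shown to precede sight of arm comparisons. The documents do not say whether those have been seen.

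**Conclusion.** The point holds as an efficiency gain on secondary outcomes. The planned estimate is valid and unbiased but less precise than it could be, because it leaves free a baseline difference that randomization fixes at zero. The common-baseline model targets the same effect.

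With equal SDs and complete data the variance falls by (1 − ρ)/2: between 45% and 5% as ρ runs from 0.1 to 0.9. If ρ is 0.4–0.6 (assumed), the fall is 20–30% and standard errors are 11–16% smaller, since 1 − √0.80 = 0.11 and 1 − √0.70 = 0.16. With an assumed 20/40% missing at 3/12 months, ρ = 0.5 gives 21%/17%. With an assumed SD ratio of 0.7 and ρ of 0.5–0.7, the gain is only 5% down to 0% under an unstructured covariance. With that covariance there is no asymptotic loss.

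The constraint is justified only where the groups compared are the randomized ones. The partner contrast in Moderator Analysis sets women in the CETA arm who included a partner against control women who said they would have. Inclusion is settled after allocation on one side only, so equal baseline means are not guaranteed there.

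**What to change.** For the randomized comparison of SVAWS, CES-D, HTQ and ASSIST:

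1. Drop the arm main effect. Use fixed effects for time (0, 3, 12 months) and arm by post-baseline time only, so that the arms share one baseline mean.
2. Replace the random intercept by an unstructured covariance across the three visits, keeping the robust standard errors.
3. Keep women who have only a baseline score in the model. A separate baseline-adjusted regression at each follow-up would drop them.
4. Do not impose the common baseline on the partner-inclusion contrast.
5. Date the change before any arm comparison of these scores is seen. If that is no longer possible, keep the planned model and report this one beside it as a labelled supplementary analysis.

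The cost is a short SAP amendment and a small change to model code. No new data are needed, and the effect estimated stays the same. The remaining cost is the documentation of timing in item 5.
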